### **8.3.3 PK analysis set**

Not applicable.

### **8.3.4 PRO analysis set**

PRO reported throughout the course of the study including findings of the standard symptoms questionnaire used at 1st Chair and Department of Cardiology and SF-12 questionnaire will be listed individually per treatment group and analyzed.

### **8.3.5 Analysis of the primary variable(s)**

Primary variable is the concentration of PEV exposing P-selectin and PS. Student's two-sided t-test or Mann–Whitney U test will be used to compare the concentrations between the two treatment arms. ANOVA-repeated measures or Friedman test will be used to compare the concentrations between the three blood samplings for PEV analysis within each group. A p-value below 0.05 will be considered significant.

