## 2. STUDY OBJECTIVES

### 2.1 Primary objective

Primary Objective:	Outcome Measure:
To compare the effects of ticagrelor and clopidogrel on the concentration of PEVs in patients with acute myocardial infarction.	Concentration of PEV exposing P-selectin and PS (flow cytometry).

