### **5. STUDY ASSESSMENTS**

#### **5.1 Efficacy assessments**

The efficacy of ticagrelor will be assessed as a decrease in the concentration of EVs, in comparison with clopidogrel.

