### 5.7 Biomarker analysis

Concentrations of PEV and other biomarkers will be analysed in citrate-anticoagulated plasma prepared according to recently standardized protocols for handling and storage of human body fluids for analysis of extracellular vesicles [14,18]. Venous blood will be collected from fasting individuals to measure concentrations of EVs and platelet aggregation. The protocol for blood collection and handling is enclosed in Appendix D. Blood sampling will be conducted in all subjects three times: (i) 24 hours following administration of loading dose of clopidogrel, (ii) 48 hours following randomisation to ticagrelor or clopidogrel group, and (iii) 6 months following the index hospitalization. PEV analysis

- Concentrations of PEVs will be determined by state-of-the art flow cytometry (Apogee A60 Micro, UK) [14]. A selection of typical PEV samples will be isolated by size-exclusion chromatography [19] and analysed by transmission electron microscopy to confirm the presence of PEV and to study PEV morphology.
- Platelet function

Platelet function will be assessed by Multiplate impedance aggregometry (Multiplate Analyzer, Roche Diagnostics, Germany) using adenosine diphosphate (ADP; 6.5 µM) and thrombin receptor-activating peptide (TRAP, 32 µM) as agonists. Methodology applied to measure platelet function enables rapid and reliable on-site evaluation of platelet function,

including monitoring of platelet inhibition in patients treated with the P2Y12 receptor antagonists [20].

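### Section 8.3.5 does not say which blood sampling, or whether level or change, decides the primary between-arm PEV comparison, and it sets no multiplicity rule

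*Combined protocol and SAP*

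**What the plan says.** Section 5.7 schedules three samplings in every subject. Sampling (i) is timed "24 hours following administration of loading dose of clopidogrel". Sampling (ii) is the first one timed from allocation, at "48 hours following randomisation to ticagrelor or clopidogrel group". Sampling (iii) is the late one, drawn "6 months following the index hospitalization".

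Section 8.3.5 defines the primary variable as the concentration of PEV carrying P-selectin and phosphatidylserine, with no time point. A t-test or Mann–Whitney test "will be used to compare the concentrations between the two treatment arms". The three samplings appear only in the next sentence, for the within-arm comparison: "ANOVA-repeated measures or Friedman test will be used to compare the concentrations between the three blood samplings for PEV analysis within each group". The error rule is: "A p-value below 0.05 will be considered significant". The Synopsis and Section 8.3.6 repeat it.

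No other section fills the gap:

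- The outcome measure in the Synopsis and Section 2.1 carries no time point.
- Section 5.1 states: "The efficacy of ticagrelor will be assessed as a decrease in the concentration of EVs, in comparison with clopidogrel". Section 8.3.1 says much the same of PEV. Neither gives a start or end sampling.
- Section 8.2 sizes the trial on one difference of 1 with SD 1, at two-sided 0.05, tied to no sampling.

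**The concern.** The 48-hour and 6-month samplings answer different questions: an early effect after the infarction, and an effect on maintenance treatment. As Section 8.3.5 is written, either result, or whichever is significant, would fit the description of the primary analysis. Two statements of what is compared also stand side by side, concentrations in Section 8.3.5 and a fall in concentration in Sections 5.1 and 8.3.1. Even at one sampling, then, two different tests fit the plan.

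The 5% error rate and 90% power in Section 8.2 describe one test. If the analysis runs over two samplings or two scales at 0.05 each, the chance of a positive primary result with no drug effect is above 5%, and a reader cannot tell from the protocol which result was meant to decide the trial.

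**Working it through.** **Inputs.** From Section 8.2: two-sided alpha 0.05, SD 1, difference 1, power 0.9, total 60. From Section 3.3: 1:1 allocation, so 30 per arm. The documents give no correlation between samplings; every value of r below is an assumption.

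**1. The plan's own figure.** The normal formula n = 2(z₀.₉₇₅ + z₀.₉₀)² × (SD/difference)² gives 2 × (1.960 + 1.282)² = 21.01, so 22 per arm. The exact t calculation gives 22.02, so 23 per arm and 46 in total. The stated 60 is therefore not reproduced from the stated inputs. Section 8.2 refers to Appendix E for the explanation, so this is not called an error; 60 is more than the inputs require. With 30 per arm the noncentrality is 1/√(2/30) = 3.87 on 58 df, and power is 0.968 at 0.05.

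**2. How many between-arm tests fit the text.** Two samplings are timed clearly after randomisation, (ii) and (iii). Sampling (i) is timed from the clopidogrel loading dose that all subjects receive and reads as a baseline, so two is the fair count.

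**3. Two samplings, each at 0.05, no drug effect.** Risk = 1 − P(|Z₁| < 1.96 and |Z₂| < 1.96), with correlation r between the two test statistics. At r = 0 this is 1 − 0.95² = 9.75%.

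| Assumed r | 0 | 0.5 | 0.7 | 0.9 |
|---|---|---|---|---|
| Risk of at least one p < 0.05 | 9.75% | 9.1% | 8.3% | 7.0% |

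Simulated t-tests with 30 per arm agree to within 0.2 of a percentage point.

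**4. One sampling, but level or change left open.** Let Y be the value at the named sampling and B the value at sampling (i), both with SD 1 and correlation r. Then Var(Y − B) = 2(1 − r) and Cov(Y, Y − B) = 1 − r, so the correlation of level with change is √((1 − r)/2).

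| Assumed r | 0.3 | 0.5 | 0.7 |
|---|---|---|---|
| Correlation of level and change | 0.59 | 0.50 | 0.39 |
| Risk if either may count | 8.8% | 9.1% | 9.4% |

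Naming the sampling without naming the scale therefore leaves a problem of about the same size.

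**5. After the fix, under the plan's inputs.**

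- One named sampling and scale: 5% risk, 96.8% power with 60 patients.
- Holm over two co-primary samplings: risk at or below 5%. The first step is at 0.025, where 30 per arm give 93.9% power. The sample size for 90% power at 0.025 is 26.12, so 27 per arm.

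**6. Gain from baseline adjustment.** The 95% CI half-width without adjustment is t₀.₉₇₅,₅₈ × √(2/30) = 2.002 × 0.258 = 0.52 SD. ANCOVA on sampling (i) multiplies the standard error by √(1 − r²), with 57 df: 0.49, 0.45 and 0.37 SD at assumed r of 0.3, 0.5 and 0.7.

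**The case against.** Section 1.2 calls the study preliminary and the Synopsis calls it proof of concept. Section 8.1 plans one final analysis by an independent statistician, and Sections 3.6 and 5.7.2 blind the operator who measures the samples. A formal error rule may look excessive for 60 patients and a biomarker. These features do protect the measurement and rule out interim looks, but they do not choose the time point or the scale, and the statistician is not stated to be blinded. The plan also declares a primary variable, a 0.05 test and 90% power, which have a meaning only for a defined test. What stands is that a multiplicity procedure is not essential in itself: once a single primary test is named, the other sampling is simply secondary.

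Appendix E and the registration may already name the sampling. That limits the claim, as set out in the verdict.

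Four stronger readings are tempting and are not supported:

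- **A risk of up to about 14%, from testing all three samplings.** This treats sampling (i) as an efficacy test, although it reads as a sample on clopidogrel alone.
- **Efficacy inferred from one arm changing significantly and the other not.** The plan does not propose this. Sections 5.1 and 8.3.1 judge ticagrelor against clopidogrel, and Section 8.3.5 has a direct between-arm test.
- **A 6-month visit with a 6-month window either side.** Section 4 prints this for Visit 5, but the table may have been broken in extraction.
- **An invalid test because it ignores baseline.** An unadjusted between-arm comparison at a post-randomisation sampling is valid. Adjustment only sharpens it.

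**Conclusion.** The point holds and should be fixed. The protocol text available does not fix the sampling or the scale of the primary between-arm test, and it sets no rule for more than one test. Testing both post-randomisation samplings at 0.05 gives a false-positive risk of about 7 to 10%, against the 5% used in Section 8.2. Leaving level or change open at one named sampling gives about 9%. Both ranges rest on assumed correlations and on the null being true at each sampling.

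A reader might infer that nothing was prespecified, or that the result will be picked after the data are seen. The documents do not show that: Appendix E and the registration are unseen. The supportable statement is that Section 8.3.5 leaves the choice open. If either source names the sampling, the section should be made to match it.

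**What to change.** In Section 8.3.5, before unblinding:

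1. **Name one primary test.** State one post-randomisation sampling (48 hours or 6 months, the sponsor's choice, consistent with the basis of Section 8.2) and one scale, tested between arms at two-sided 0.05. Preferably use ANCOVA of PEV at that sampling with sampling (i) as covariate, on the log scale if skewed, with a 95% CI. This needs confirmation that sampling (i) precedes the first randomised dose, which Section 5.7 does not state. Without it, compare levels unadjusted, because adjusting for a post-dose value could remove part of the drug effect. Align the efficacy wording in Sections 5.1 and 8.3.1.
2. **Give the other sampling its place.** Make it secondary, tested only if the primary is significant. Use Holm over the two only if the sponsor wants both as co-primary. State that sampling (i) is baseline and not an efficacy test.

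Recommended only: label the within-arm ANOVA and Friedman results descriptive, and check the Visit 5 window in Section 4 against the source document.

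Cost: a short protocol amendment, notified to the ethics committee under Section 10.5, and, for ANCOVA, a check of when sampling (i) was drawn and one degree of freedom. No extra patients or samples are needed.

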## **1. INTRODUCTION**

### **1.1 Background and rationale for conducting this study**

Platelet activation and aggregation in response to atherosclerotic plaque rupture is a key event in the pathogenesis of acute myocardial infarction (AMI) [1]. Platelet P2Y12 receptors for adenosine diphosphate are essential for platelet activation [2], and from this reason antagonists against the P2Y12 receptor are established in secondary prevention of cardiovascular events [3]. Beyond blocking platelet activation, antagonists of the P2Y12 receptor have hitherto unexplained anti-inflammatory effects [4,5]. Findings from the PLATelet inhibition and patient Outcomes (PLATO) study demonstrated that platelet inhibition with a novel and potent P2Y12 receptor antagonist ticagrelor reduced mortality following pulmonary infections and sepsis compared to clopidogrel, previous standard treatment for patients with AMI [5].

Activated platelets release platelet extracellular vesicles (PEV) [6]. PEV differ from other biomarkers of inflammation and platelet activation, because (i) PEV are released from activated platelets at the early stage of developing arterial thrombosis [7], (ii) PEV expose specific platelet antigens and thus can be identified as being platelet-specific [8], (iii) PEV participate both in inflammation and in coagulation due to exposure of P-selectin and phosphatidylserine (PS) [9,10]. P-selectin initiates binding of platelets and/ or PEV to leukocytes which leads to leukocyte activation and secretion of cytokines [9], and (ii) PS and other negatively charged phospholipids bind positively charged clotting factors thereby propagating thrombin generation [10]. Additionally, PEV serve as pro-inflammatory stimuli in acute lung injury [11], which is one of the leading causes of death in sepsis [12]. Because identification and characterization of PEV directly in human plasma has recently become feasible [13], and because PEV can be measured in biorepositories thereby facilitating validation in multicentre clinical trials [14], it is likely that the requirements for PEV to become a reliable biomarker can now be fulfilled.

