#### **4. STUDY PLAN AND TIMING OF PROCEDURES**

Visit	1	2	3	4	5	No follow-up	For details see Protocol Section
Visit window							
Day -1 to 0 for Visit 1							
±1 day for Visit 2							
±3 days for Visit 3							
±5 days for Visit 4							
± 6 months for Visit 5							
Week		0	1			24	
Day	-	0	1	3	5	168	
Written informed consent	X						
Demographics	X						
Physical examination, height, and weight	X		X	X	X	X	

Visit	1	2	3	4	5	No follow-up	For details see Protocol Section
Visit window							
Day -1 to 0 for Visit 1							
±1 day for Visit 2							
±3 days for Visit 3							
±5 days for Visit 4							
± 6 months for Visit 5							
Week		0	1			24	
Day	-	0	1	3	5	168	
Medical/surgical history	X						
Inclusion/exclusion criteria	X	X					
12-lead ECG	X		X	X	X	X	
Vital signs	X	X	X	X	X	X	
Randomisation to study treatment		X					
Treatment dispensed/returned		X				X	
Concomitant medication	X	X	X	X	X	X	
Adverse event review (AEs and SAEs)		X	X	X	X	X	

Visit	1	2	3	4	5	No follow-up	For details see Protocol Section
Visit window							
Day -1 to 0 for Visit 1							
±1 day for Visit 2							
±3 days for Visit 3							
±5 days for Visit 4							
± 6 months for Visit 5							
Week		0	1			24	
Day	-	0	1	3	5	168	
Blood samples for haematology and clinical chemistry	X			X		X	
Urinalysis	X			X		X	
Blood sampling for pharmacokinetics		n.a.	n.a.	n.a.	n.a.	n.a.	

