#### **5.2 Safety assessments**

##### **5.2.1 Laboratory safety assessments**

*Table x                      Laboratory Safety Variables*

---

Haematology/Haemostasis (whole blood)	Clinical Chemistry (serum or plasma)
B-Haemoglobin (Hb)	S/P-Creatinine
B-Leukocyte count	S/P-Aspartate transaminase (AST)
B-Platelet count	S/P-Alanine transaminase (ALT)
	S/P-Potassium
	S/P-Sodium
Urinalysis (dipstick)	
U-Hb/Erythrocytes/Blood	
U-Protein/Albumin	
U-Glucose	

---

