## **8.2 Sample size**

Because there is no sufficient data to assess the impact of ticagrelor on the concentrations of PEV in patients with AMI, the SD and mean difference between the groups was estimated based on the preliminary experiments, which we conducted in during preparation for this study. The required sample size was calculated by a two-sided t-test at a significance level of 0.05 with the following assumptions: (i) SD in each group  $\pm 1$ , (ii) mean difference between the groups = 1, (iii) nominal test power = 0.9. Based on this sample size estimation, it is calculated that a total of 60 patients will be enrolled in the trial. The conference abstract [15], as well as the explanation on how the sample size has been calculated are included in Appendix E.

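### The primary between-arm PEV test uses no baseline covariate, although suitable values are scheduled; prespecified adjustment would be a low-cost, probably modest gain in precision

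*Combined protocol and SAP*

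**What the plan says.** The outcome is defined in Section 8.3.5: "Primary variable is the concentration of PEV exposing P-selectin and PS". The between-arm analysis follows: a two-sided t-test or a Mann–Whitney test "will be used to compare the concentrations between the two treatment arms". No covariate is named, and the section does not say which of the three samplings the comparison uses. Repeated-measures ANOVA or Friedman tests are planned only within each arm, so the first sampling does not enter the between-arm comparison as a baseline. Sensitivity and exploratory analyses (Sections 8.3.9 and 8.3.10) are marked not applicable, so no adjusted analysis appears elsewhere.

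Two candidate baseline values are already scheduled:

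- **Platelet count.** Section 5.2.1 lists "B-Platelet count" among the laboratory safety variables. The Section 4 schedule marks "Blood samples for haematology and clinical chemistry" at Visit 1 (window Day -1 to 0), and randomisation at Visit 2 (Day 0).
- **First PEV sample.** Section 5.7 times it 24 hours after the clopidogrel loading dose. The second sample is timed 48 hours after randomisation and the third at 6 months.

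Section 1.1 attributes PEV release to activated platelets. Section 3.3 describes 1:1 block randomisation and mentions no stratification.

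**The concern.** The outcome is a concentration of platelet-derived vesicles, so a patient's baseline PEV level, and possibly the platelet count, may predict the later value. If so, an unadjusted comparison leaves explainable between-patient variation in the error term. With 30 per arm and no stratification, nothing in the design balances these values, and a chance difference between arms carries over in part to the PEV estimate. Both can be reduced with data the trial already plans to collect.

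The choice should be made before unblinding, because a covariate added afterwards would look data-driven.

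**Working it through.** **1. The plan's own figure.** Section 8.2 uses a "two-sided t-test at a significance level of 0.05" and "nominal test power = 0.9", with SD 1 and difference 1.

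- Normal approximation: n per arm = 2 × (1.960 + 1.282)² × (1/1)² = 21.01, rounded up to 22, or 44 in total.
- Exact noncentral t: 22 per arm gives power 0.8997 and 23 gives 0.912, so 46 in total.
- The planned 60 is larger than these inputs require. Appendix E, said to explain it, is not in the supplied text, so 60 is not shown to be wrong. The steps below take 30 per arm as given.

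**2. Unadjusted power with 30 per arm.** Noncentral t, two-sided 0.05, 58 df, noncentrality d/√(2/30), where √(2/30) = 0.258.

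- d = 1 SD (planned): 1/0.258 = 3.87, power 0.968.
- d = 0.75 SD (an illustration, not in the documents): 0.75/0.258 = 2.90, power 0.815.

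**3. Variance after adjusting for one baseline covariate.** Let r be the within-arm correlation of covariate and outcome. It is an assumption, shown over 0 to 0.5. Residual variance falls to 1 − r². Estimating the slope costs, on average, a factor (N − 3)/(N − 4) = 57/56 = 1.018 at N = 60. Net variance relative to the unadjusted test is therefore (1 − r²) × 57/56.

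Break-even is where 1 − r² = 56/57, so r = √(1/57) = 0.13. Below that, adjustment loses slightly.

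**4. Adjusted power.** The noncentrality becomes d/√(net variance × 2/30), with 57 df.

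| r | Net variance | Power at 0.75 SD | Power at 1 SD |
|---|---|---|---|
| Unadjusted | 1 | 0.815 | 0.968 |
| 0 | 1.018 | 0.808 | 0.965 |
| 0.2 | 0.977 | 0.823 | 0.971 |
| 0.3 | 0.926 | 0.843 | 0.977 |
| 0.5 | 0.763 | 0.905 | 0.992 |

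**5. Chance imbalance.** The difference in covariate means between arms has a standard error of √(2/30) = 0.258 SD and a 95% range of ±1.96 × 0.258 = ±0.51 SD. Carry-over to the unadjusted estimate is r times that: up to 0.10 outcome SD at r=0.2, 0.15 at r=0.3 and 0.25 at r=0.5, against a planned effect of 1 SD.

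**6. Which covariate is safe.** The Visit 1 platelet count precedes randomisation by schedule. The first PEV sample is the outcome's own early value and the more natural covariate, but its timing is tied to the clopidogrel load and not to randomisation. The Section 4 table as supplied has no row for PEV sampling, and the Section 1.3 flow chart is not visible in the supplied text. If that sample can follow the first dose of randomised drug, adjusting for it could remove part of the treatment effect.

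**The case against.** The case against is substantial.

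- **The benefit is not documented.** No section gives r. Section 1.1 speaks of activated platelets, and the endpoint is the subset exposing P-selectin and PS. Being the source of the vesicles does not make platelet number a predictor of that subset. If the 6-month sample is meant, an acute-phase count would have to predict a value half a year later. This stands, and it is why only a range can be given.
- **Power is already high.** At the planned 1 SD the gain is under one percentage point when r is 0.3 or less. This also stands. But Section 8.2 concedes that data on the effect are insufficient and relies on preliminary experiments, so the planned effect is not assured.
- **A log-scale linear model is a further change.** It replaces the choice between a t-test and a rank test, and it cannot be run until a sampling time is named. Both belong in the fix.

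A reader might infer that adjustment is free precision. It is not: at r=0 it costs 1.8% in variance and about 0.7 points of power at 0.75 SD (0.815 to 0.808).

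A reader might also infer that the planned test is invalid or biased. The documents do not support that either. Allocation is randomised, and chance imbalance is already reflected in the unadjusted standard error; what suffers is precision, and the accuracy of the estimate in a trial that happens to be imbalanced.

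**Conclusion.** The point holds as an improvement to the plan, not as a defect in validity. The primary between-arm test ignores baseline information that the schedule already provides, and no adjusted analysis is planned anywhere.

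The trade-off favours adjustment. The worst case for one covariate is about 2% more variance. The gain is about 2% less variance at r=0.2, 7% at r=0.3 and 24% at r=0.5. In power, that is at most 2.4 points at the planned effect (0.968 to 0.992 at r=0.5) and 9.0 points at 0.75 SD (0.815 to 0.905).

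These figures assume 30 analysed per arm, an approximately linear relation on the analysis scale, and the stated range of r. The documents do not establish that platelet count predicts PEV concentration, or that the first PEV sample precedes the randomised drug.

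**What to change.** In Section 8.3.5:

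1. Name the post-randomisation sampling that the primary between-arm comparison uses.
2. Make that comparison an ANCOVA on log PEV concentration, with arm and pre-randomisation covariates as terms.
3. Use the first PEV value as covariate if it is confirmed to be drawn before the first dose of randomised drug, and add the Visit 1 platelet count. If that timing cannot be confirmed, use the platelet count alone.
4. Report the adjusted ratio of geometric means with its 95% CI, and keep the unadjusted test as supporting.
5. Do not adjust for platelet counts taken after randomisation, since treatment may affect them.
6. State how a missing baseline value is handled.

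The cost is a few sentences in the plan and no new data. The downsides are one or two of the 58 degrees of freedom, reliance on a log-scale linear model, and up to about 2% more variance for each covariate that proves not to be prognostic.

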#### **3.9.1 Procedures for discontinuation of a subject from investigational product**

For subjects discontinued from the IP, the same measurements and assessments will be performed as in patients continuing the study until the last visit at 6 months, including monitoring of the adverse events. The subjects will be asked to return the study medication.

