### **3.10 Criteria for withdrawal**

Criteria for withdrawal from the study include:

- Withdrawal of informed consent.

- Development of exclusion criteria, pregnancy or other safety reasons during the study (requirement of unacceptable concomitant medication, adverse event, intolerance of the investigational product).
- Protocol non-compliance.
- Incorrect enrolment or randomization of the subject.
- Lost to the last visit at 6 months.
- Any other reason, in the investigator's opinion, that would impede the subject's participation in the study

The withdrawn subjects will be replaced by subjects subsequently recruited for the study, until the estimated sample size of the study participants will be achieved.

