## 8. STATISTICAL ANALYSES

### 8.1 Statistical considerations

A single statistical analysis will be performed at the end of the study by an independent professional statistician from the Epidemiology Department of Medical University o Warsaw using IBM SPSS Statistics 20 and GraphPad Prism 5. An intention to treat (ITT) approach

will followed, i.e. statistical analysis will be based on data from all patients who were randomized and from whom meaningful data were collected. Data will be displayed graphically for visual inspection. Categorical variables will be presented as number and percent; continuous variables will be presented as mean and standard deviation (SD) or median with inter-quartile range. Shapiro–Wilk test will be used to test for non-Gaussian distribution of continuous variables.

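### The within-arm time analysis keeps only subjects with all three samples; this sits uneasily with section 8.1, and the plan gives no rule for a missing sample

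*Combined protocol and SAP*

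**What the plan says.** - **Sampling (section 5.7).** "Blood sampling will be conducted in all subjects three times": 24 hours after the clopidogrel loading dose, 48 hours after randomisation, and at 6 months.
- **Time comparison (8.3.5, repeated in 8.3.6).** "ANOVA-repeated measures or Friedman test will be used to compare the concentrations between the three blood samplings for PEV analysis within each group", judged at p below 0.05.
- **Between-arm comparison (8.3.5).** "Student's two-sided t-test or Mann–Whitney U test will be used to compare the concentrations between the two treatment arms".
- **Analysis principle (8.1).** Intention to treat, explained as: "statistical analysis will be based on data from all patients who were randomized and from whom meaningful data were collected". The qualifier *meaningful* is not defined.
- **Loss at the last visit (3.10).** "Lost to the last visit at 6 months" is a criterion for withdrawal, and "The withdrawn subjects will be replaced by subjects subsequently recruited for the study".
- **Stopping the product (3.9.1).** For these subjects "the same measurements and assessments will be performed as in patients continuing the study until the last visit at 6 months".
- **Withdrawn sample consent (5.7.4).** Samples from these subjects are left out of the analysis.

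No section says what happens when one of the three samples is missing. Section 8.3.1 restates the efficacy measure without defining a population, and section 8.3.9 plans no sensitivity analysis.

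**The concern.** Repeated-measures ANOVA and the Friedman test, as usually run, work on complete blocks. If one of three values is absent, the other two go with it. The 24-hour to 48-hour contrast then loses subjects who have both of those values, only because a third sample six months later was not taken.

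This has two consequences. First, section 8.3.5 would report results on different subjects: everyone sampled for the between-arm test at a given time, but completers only for the time analysis. Nothing in the plan tells the reader so. Second, if loss at 6 months is related to earlier vesicle concentrations, the completers are a selected group and the estimated time course is distorted. The time analysis is specified for the primary variable and for every secondary variable, so the gap recurs across the results.

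**Working it through.** **Inputs from the documents.** Total N = 60 with 1:1 allocation (8.2, 3.3), so 60 / 2 = 30 per arm. Three samples per subject (5.7). The plan gives no figure for the time analysis and no missing-sample rate. For completeness, the assumptions in 8.2 (SD 1, difference 1, two-sided 0.05, power 0.9) give 22.02, rounded up to 23 per arm or 46 in total by the exact t-test, so they do not by themselves reproduce 60. The explanation is said to be in Appendix E, which is not in the available text. This does not bear on the present point.

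**Step 1: behaviour of the named tests.** Both were run on 30 subjects by three times with one value removed. The repeated-measures ANOVA routine stopped because the data were unbalanced. The Friedman routine rejected unequal lengths, and returned no statistic when the gap was coded as missing. Neither can use an incomplete triplet.

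**Step 2: assumptions.** Only the 6-month sample is missing, since the two early samples fall close to the index admission. Loss d is 5, 10, 15 or 20%. The chance of loss rises with the 48-hour value (logistic, slope 1 per SD). Correlation between any two samples is 0.5, and there is no true change over time. Values are in SD units. Results come from 2,000,000 simulated subjects per scenario.

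**Step 3: results.** Complete subjects per arm = 30 × (1 − d). The contrast bias is the shift at 48 hours minus the shift at 24 hours or 6 months. The SD of a change is √(2 × (1 − 0.5)) = 1, so its standard error is 1/√n.

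| Loss at 6 months | Complete per arm | Shift in completers' 48 h mean | Shift at 24 h and at 6 months | Bias in 24 h–48 h and 48 h–6 months contrasts (absolute) | Standard error | Bias / SE |
|---|---|---|---|---|---|---|
| 5% | 28.5 | −0.047 | −0.024 | 0.023 | 0.187 | 0.12 |
| 10% | 27.0 | −0.091 | −0.047 | 0.045 | 0.192 | 0.23 |
| 15% | 25.5 | −0.132 | −0.068 | 0.065 | 0.198 | 0.33 |
| 20% | 24.0 | −0.174 | −0.088 | 0.086 | 0.204 | 0.42 |

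The 24-hour to 6-month contrast is essentially unbiased here, because both means shift equally.

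**Step 4: the alternative.** When only the last sample is missing, a likelihood fit takes the 24-hour and 48-hour means from all 30 subjects and predicts the 6-month mean from the earlier values. In the same simulation its bias at 6 months was 0.001 SD or less. The standard error of the 24-hour to 48-hour contrast becomes 1/√30 = 0.183, against 0.187–0.204 for completers. The gain in precision is small; the main gain is removal of the bias.

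**The case against.** The strongest reply has four parts.

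1. **Section 8.1 does not promise to use every sample.** It is limited to patients with meaningful data. A reader might infer a flat contradiction with intention to treat, but the documents do not support that: if the sponsor counts only full series as meaningful, there is none. This stands. Two assayed samples from a randomised patient are meaningful on a natural reading, so tension remains.
2. **Loss at 6 months is dealt with openly.** Section 3.10 withdraws and replaces such subjects, so it would be wrong to say that all of this loss goes unmentioned, and the fall in numbers may be made up. This stands for the headcount. However, replacements who complete do not undo the selection of completers, 3.10 does not say that earlier samples leave the analysis, and a missed or unusable early sample is not covered.
3. **Subjects who stop the product are still measured to 6 months (3.9.1).** This weakens the argument that intolerance leads to missing samples. It stands in part, because 3.10 lists much the same reasons as grounds for withdrawal and replacement. The two sections need to be reconciled.
4. **The treatment comparison is untouched.** A reader might infer that the primary between-arm result is compromised. It is not: the t-test or Mann–Whitney test can use every subject sampled at the time tested.

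A reader might also take the 0.05–0.17 SD shift in the completers' 48-hour mean as the size of the problem. The criticised tests compare samplings, and about half of that shift cancels in the contrasts.

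**Conclusion.** The point holds for the within-arm time analysis only. As written, 8.3.5 and 8.3.6 lead to a complete-series analysis that the plan neither states nor justifies, and that fits poorly with the most natural reading of 8.1. It is a gap and a tension, not a proven contradiction.

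The likely effect is modest: 28.5 down to 24 complete subjects per arm before any replacement, and bias of about 0.02–0.09 SD in the time contrasts, or roughly 0.1–0.4 of a standard error. These figures rest wholly on the assumed 5–20% loss at 6 months, its dependence on the 48-hour value, and the correlation of 0.5. If loss is unrelated to vesicle concentration, the cost is precision alone. The bias is avoidable at little cost, which is why a change is worth making.

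**What to change.** In 8.3.5 and 8.3.6:

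- Replace the within-arm test with a likelihood-based linear mixed model fitted to every available sample from all randomised subjects, with sampling as a fixed factor and an unstructured within-subject covariance. Use log concentration if the data are skewed.
- Keep Friedman on complete series as a supportive check.
- Report the number of subjects contributing at each sampling, by arm.

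In 8.1, define meaningful data and give the missing-sample rule: earlier samples of subjects lost at 6 months stay in the analysis unless sample consent is withdrawn (5.7.4). Reconcile this with the withdrawal and replacement text in 3.10, and reconcile 3.10 with 3.9.1.

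The cost is plan wording and a little more analysis work. The model relies on approximate normality, possibly after log transformation, and on loss depending only on observed values. Section 8.1 names "IBM SPSS Statistics 20 and GraphPad Prism 5"; the statistician should confirm which package will fit the model.
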